3.5 Data collection, clinical examinations and evaluation of results

In this project, wearable devices such as the Galaxy Watch will be used. 5 together with Galaxy series smartphones (A or S line) for the acquisition of blood pressure measurements, arterial hemoglobin oxygen saturation (SpO2), heart rate and ECG. This data will be transmitted to a repository, in a secure cloud environment, which meets the requirements of the General Data Protection Act

(LGPD) (Figure 5). In addition, data will be transmitted to a platform to be developed by InCor's IT team, as part of the project, and integrated into InCor's electronic medical record through the WebAdmin tool .

[figure not shown]

Figure 5 . Conceptual diagram for the Telemonitoring Platform.

The division of the study into phases and activities was carried out according to the table and description below.

Phase	Local	Activity
Phase 1	outpatient	
 • Inclusion of patients • Preoperative consultation; • Meeting with the project coordination team; • Complete anamnesis; • Application of the TCLE; • Collection of additional and contact information;
Level 2	hospitalization	
 • Hospitalization; • Eventually, some patients may be included in the study after hospitalization, prior to surgery, with the application of informed consent at this time;
phase 3	surgical	
 • Performing the surgical procedure; • Intraoperative data collection; • Postoperative evaluation and discharge • Patient guidelines; • Signature of the equipment loan liability term (smartphone and smartwatch); and the term for using data from the Electronic Health Record; • Calibration: 
 - BP, serial measurements - smartwatch SAMSUNG + traditional auscultatory method; - ECG - smartwatch SAMSUNG + traditional ECG; - SpO2 - SAMSUNG smartwatch oximetry + traditional oximetry; • Questionnaire of events observed during the remote phase;

Phase 4	remote collection	
 Tracking, monitoring and managing each participant's remote data collection for 30 ± 3 days; these being: 
 - Automatically collected: SpO2, heart rate, steps and sleep. - Collected manually: blood pressure and ECG. Telephone contact, teleconsultations, and unscheduled face-to-face consultations in cases of complications;

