3.8 Traditional electrocardiography (ECG) *versus* SAMSUNG smartwatch ECG

Still in phase 3 of the project, resting electrocardiography (ECG) tests will be performed in conjunction with ECG collection from the *smartwatch SAMSUNG*, for comparison between the two analysis methods (gold standard vs. device).

All electrocardiograms will be performed at a speed of 25mm/ sec, with 1mV/10mm calibration, in a MAC 2000 ECG Machine (GE Medical Systems Information Technologies, Inc., WI, USA) on an outpatient basis. The electrodes will be placed in the classic way of 12 leads (6 in the frontal plane D 1,D 2,D3,aVr,aVl,aVf and 6 in the horizontal plane V1,V2,V3.V4,V5,V6). The parameters will be evaluated by the clinical cardiologist, who will issue a report, based on the guidelines of the Brazilian Society of Cardiology on analysis and issuance of electrocardiographic reports.

3.9 Peripheral oxygen saturation (SpO₂) measurement by SAMSUNG *smartwatch* versus standard oximetry

SpO₂ values will be measured simultaneously by the *smartwatch* **SAMSUNG** and a digital pulse oximetry equipment (G-TECH 302L). Traditional oximetry, using an infrared light beam, simultaneously measures heart rate and peripheral oxygenation in percentages of 0-100%, and measurements above 95% will be considered normal. This evaluation will be carried out in phases 3 and 5 of the project.

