3.10 Blood pressure (BP) measurement by SAMSUNG *smartwatch* versus standard device

smartwatch will first be calibrated **SAMSUNG** for BP measurement following the instructions of the equipment itself. From then on, 8 consecutive measurements will be taken, at rest, alternating between using the *smartwatch* **SAMSUNG** and the arm pressure gauge (Brand *Welch*) standard, which uses aneroid meter and pulse auscultation (stethoscope *littman clinic*). Measurements with the standard device will be performed with the patient in the supine position, after 10 minutes of rest with 3 consecutive measurements. Additionally, a measurement will be performed in a sitting position and another measurement in an orthostatic position with a 30-second difference between measurements.

This assessment will be repeated in phase 5 of the project, following the same methodology described above.

3. 11 Definition of alerts – teleassisted group

The multidisciplinary team will receive alerts through the application platform, according to pre-established limits of blood pressure, heart rate and blood oxygen saturation.

- Blood pressure

Normal Parameters: Systolic [100 – 140 mmHg] and diastolic [70-90 mmHg]

Yellow Alert: Systolic [100 – 180 mmHg] and diastolic [90 – 110 mmHg]

Red Alert: Systolic [<90 and >180 mmHg] and diastolic [<60 mmHg and >100 mmHg].

- Heart Rate:

Normal parameters: HR detection between 60-100 bpm.

Red Alert: Detection of HR < 50 bpm outside sleep period; or HR > 100 bpm (concurrently assessed by watch)

- Oxygen Saturation:

Normal parameters: 95 – 100%

Yellow Alert: 91 – 95%

Red Alert: <90%

The conduct and actions planned to be taken by the clinical team after receiving the alerts through the Si3 platform (on D+1), as well as the guidelines that teleassisted patients will receive at the time of hospital discharge, are described in the table below:

INFORMAÇÕES AO PACIENTE

INFORMAÇÕES À EQUIPE CLÍNICA

[figure not shown]
	SITUAÇÃO	ORIENTAÇÃO	INTERVENÇÃO	AÇÃO
	Detecção de FC < 50 bpm fora do período de sono	Realizar medidas de parâmetros indiretos (ECG, P.A. E SPO ²)	Entrar em contato com a enfermeira da equipe pelo telefone	Analisar os parâmetros clínicos e os sintomas do paciente. Enfermeira aciona teleconsulta com o médico se necessário. Em caso de necessidade, o médico orienta o paciente a procurar o PS do InCor

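### The SpO2 alert limits in 3.11 and Table 2 leave a reading of 90% with no alert and no planned action, although 91% and 89% both trigger one.

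*Combined protocol and SAP*

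**What the plan says.** Section 3.11 bases the remote safety alerts on fixed limits: "The multidisciplinary team will receive alerts through the application platform, according to pre-established limits of blood pressure, heart rate and blood oxygen saturation". For oxygen saturation it gives three lines, all in per cent: "Normal parameters: 95 – 100", then "Yellow Alert: 91 – 95", then a red alert for values strictly below 90.

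Table 2 turns the two alert bands into actions, in Portuguese. The 91 to 95% row has the patient contact the team nurse, who reviews the clinical picture and arranges a teleconsultation if needed. In the row for values below 90% the patient also contacts the nurse and is directed to the InCor emergency department. There is no other SpO2 row. Section 3.11 introduces this table as covering both what the clinical team does and what patients are told at discharge.

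Two other places bear on the point. Table 1 in section 3.5 lists SpO2 among the signals the watch gathers without patient action in Phase 4: "Automatically collected: SpO2, heart rate, steps and sleep". Section 3.9, on the comparison with standard oximetry, states that "measurements above 95% will be considered normal".

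**The concern.** An alert rule should assign every possible reading to exactly one category, and its response should not weaken as the reading worsens. The SpO2 rule fails on both counts at 90%. Yellow stops at 91 and red starts strictly below 90, so the value between them has no category. A patient at 91% gets nurse contact and clinical review, and a patient at 89% is referred to the emergency department. A patient at 90%, worse than the first and close to the second, is given no response.

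Saturation is one of the three inputs that 3.11 names for the alerts, and it is collected automatically over the 30 ± 3 days at home after cardiac surgery. If the limits are coded as written, a 90% reading would raise no flag. Because Table 2 also holds the discharge guidance, the gap reaches the patient's instructions as well as the team's.

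There is a smaller defect at the upper end: 3.11 puts 95% in both normal and yellow.

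**Working it through.** No sample size, power or error rate is involved. The check is to classify every possible reading against the printed limits.

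**Inputs**
- Section 3.11: normal if 95 ≤ s ≤ 100; yellow if 91 ≤ s ≤ 95; red if s < 90.
- Table 2: intermediate row if 91 ≤ s ≤ 95; low row if s < 90.
- Scale: per cent from 0 to 100, as 3.9 gives for standard oximetry. Whole-number reporting is an assumption, since the watch's resolution is not stated.

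**Readings around the boundaries**

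| Reading | Band in 3.11 | Row in Table 2 |
|---|---|---|
| 89% | red | below 90%: emergency department |
| 90% | none | none |
| 91% | yellow | 91 to 95%: nurse review |
| 94% | yellow | 91 to 95%: nurse review |
| 95% | normal and yellow | 91 to 95%: nurse review |
| 96% | normal | none (no action needed) |

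**Count over the 101 whole numbers from 0 to 100, section 3.11**
- Red only, 0 to 89: 90 values.
- Yellow only, 91 to 94: 4 values.
- Normal only, 96 to 100: 5 values.
- Exactly one band: 90 + 4 + 5 = 99. In two bands: 1 (95%). In none: 1 (90%). Total 99 + 1 + 1 = 101.

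**Count for Table 2, whole numbers at or below 95**
- There are 96 values (0 to 95). The low row takes 90 and the intermediate row takes 5, so 95 have a row. The one left over is 90%.

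**If readings were reported to 0.1% (assumption)**
- The uncovered readings in 3.11 are 90.0, 90.1, ..., 90.9, which is 10 values.

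**Which way 95% should go**
- Section 3.9 counts only values above 95% as normal, and Table 2 includes 95% in its intermediate row. Both point to yellow, so only the lower end of the normal line in 3.11 needs changing.

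**Test of the repaired bands: normal s > 95, yellow 90 < s ≤ 95, red s ≤ 90**
- Whole numbers: red 91 (0 to 90) + yellow 5 (91 to 95) + normal 5 (96 to 100) = 101, each in exactly one band.
- Steps of 0.1%: red 901 (0.0 to 90.0) + yellow 50 (90.1 to 95.0) + normal 50 (95.1 to 100.0) = 1,001, each in exactly one band.
- Changing red to s ≤ 90 while leaving yellow at 91 to 95 would suffice for whole numbers. With decimals it would still miss 90.1 to 90.9%.

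**The case against.** The gap in the wording is not in dispute; its consequence is. Four arguments deserve weight.

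- **Repeated readings.** The watch is worn day and night for about 30 days. A patient whose saturation is falling would plausibly also give readings at 91 to 95% or below 90%, and either would trigger action. This is fair, and it limits how often a patient would be missed altogether. But the sampling frequency is not stated, so it cannot be relied on, and it does not make the rule right for the reading in question.
- **Other routes to review.** Section 3.4 has the multidisciplinary team follow the collected parameters, Table 1 lists telephone contact and teleconsultations, and the ethics text before section 4 describes checking events close to real time. Section 3.11 places the team's response to alerts on the following day, so the alert is not an immediate rescue. These are real safeguards. Even so, a reading that raises no alert is less likely to be looked at, and Table 2 would give the reviewer no instruction for it.
- **The platform may be coded sensibly.** The Si3 screens are shown in figures that could not be seen, so the documents cannot show that the software stays silent at 90%. That stands: the finding concerns the written rule. The written rule is nevertheless what the platform should be tested against.
- **It is one integer, and the blood pressure lines are worse.** In 3.11, systolic 90 to 99 and diastolic 60 to 69 mmHg have no band, the systolic yellow range contains the whole normal range, and diastolic red begins above 100 where Table 2 has above 110. This is correct. It is a reason to repair those lines in the same edit, not to leave the SpO2 gap open.

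A transcription fault is unlikely, because the same limits appear in English in 3.11 and in Portuguese in Table 2. A deliberate no-alert zone is not credible between two action zones.

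**Conclusion.** The concern holds. As written, an SpO2 reading of 90% triggers no alert and has no care row, while the better reading of 91% and the worse reading of 89% both lead to action. Nothing in the available text assigns 90% elsewhere.

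The size is one uncovered value on a whole-number scale, or ten (90.0 to 90.9%) on the unstated assumption of 0.1% reporting. The documents give no distribution of readings, so the number of patients or alerts affected cannot be estimated. The safety consequence depends on the limits being followed literally. No bearing on the re-hospitalization, adherence or device-accuracy results is claimed. Because this is a decision threshold for patients at home after cardiac surgery, it should be corrected, though it does not threaten the trial's conclusions. The double listing of 95% is tidying only.

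**What to change.** Restate the SpO2 bands identically in 3.11, Table 2 and the Si3 configuration, so that they meet without gaps or overlaps. A workable version is:

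- normal: above 95%
- yellow: above 90% up to and including 95% (the same as 91 to 95% if only whole numbers are reported)
- red: 90% or below

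The clinical team should decide whether 90% belongs in red or yellow. If yellow, use 90 to 95% for yellow and keep red strictly below 90%, which also closes the gap with decimal readings. State the reporting resolution of the device. Before first use, run every whole-number SpO2 value through the platform, and decimals if they are reported, and confirm that each returns exactly one category and the matching action.

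In the same edit, label a waking heart rate of 50 to 59 bpm as a no-alert range. It lies outside the stated normal range but loses no alert as written. The blood pressure bands should be reconciled between 3.11 and Table 2 at the same time.

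For SpO2 the cost is a wording change in two places and a short software check. The downside is slightly more alerts: additional emergency referrals if 90% is placed in red, or additional nurse contacts if it is placed in yellow.

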be submitted to the CAPPesq Research Ethics Committee, via Plataforma Brasil. The ethical aspects of research involving human beings will be considered, as recommended by Resolution 466/2012. All data collected from volunteers will be treated ensuring confidentiality and meeting the other requirements established by the LGPD. The patients will be monitored by the multidisciplinary team via SI3, and any intercurrentence verified by the multidisciplinary team in a “near real time” period and the patient will be consulted and guided in the face of the detected intercurrentences.

After completing the survey, the data will be anonymized and analyzed by the InCor team. The raw data will be made available to the contracting company without any identification of the patient. After processing and analyzing the data, publication of the results in scientific databases is expected.

4. ESTIMATED SCHEDULE

ACTIVITIES	1st month	2nd month	3rd-7th month	8th month	9th month	10th-12th month
Clinical PT submission to the Scientific Committee and CAPPesq	x					
Analysis of the Clinical PT by the Research Ethics Committee	x	x				
Device Software Installation and Testing			x			
Execution of the Clinical Protocol (inclusion of patients and remote monitoring)			x			
Compilation and analysis of results				x		
Final report				x	x	
Accountability					x	
Submission of scientific articles						x

5. ANNEXES

5.1. Case Report Form (CRF)

CASE REPORT FORM
 
Study Title
 
Wearable -assisted digital telemonitoring of post-cardiovascular surgery patients
 
Study Samsung FAPO-x

CLINICAL TRIAL/UNIT: INOVA InCor
 
PRINCIPAL INVESTIGATOR: [name] [name]
 
EXECUTING RESEARCHER: Dr. _____

I am confident that the information provided on this case registration form is complete and accurate. I confirm that the study was conducted in accordance with the protocol and any changes to the protocol and that written informed consent was obtained prior to the study .
																			
Investigator Signature:	_____																		
	
Patient Name
 
_____
																		
Patient Signature:	_____																		
Signing date:	

									

D	d	m	m	m	Th	Th	Th	Th	

										D	d	m	m	m	Th	Th	Th	Th
D	d	m	m	m	Th	Th	Th	Th											

Inclusion criteria

Yes No

- | | | | |
|----------|-----------------------------------------------------------------------------|--------------------------|--------------------------|
| 1 | Is the subject older than 22 years old with heart disease ? |  |  |
| 2 | Did the subject voluntarily give written informed consent? |  |  |
| 3 | Does the subject agree to adhere to the study procedures? |  |  |
| 4 | Does the subject have surgical indication in the presence of heart disease? |  |  |
| 5 | |  |  |

*If any inclusion criteria is marked as no, the patient is not eligible for the study.

Exclusion criteria

Yes* No

- | | | | |
|----------|----------------------------------------------------------------------------------------------------------------|--------------------------|--------------------------|
| | | _____ | _____ |
| 1 | Did the subject have post-surgical complications with an extension of the hospital stay for more than 14 days? |  |  |
| 2 | Does the subject have any skin pathology or skin diseases? (ex : vitiligo, lupus and/or atopic dermatitis) |  |  |
| 3 | Does the subject have allergies to the material components of the mobile device? |  |  |
| 4 | Does the subject have significant abrasions on the body? |  |  |
| 5 | For some reason did the patient not undergo cardiac surgery? |  |  |
| | | _____ | _____ |

VISIT 1 (TRIAGE)

Date: _____
DD MMM YYYY

INFORMED CONSENT

Note: Written informed consent must be given before any study-specific procedures occur or any current therapy is discontinued for the purposes of participation in this study.

Did the subject freely give written informed consent? Yes No

DEMOGRAPHIC DATA

Age years: Fri: Feminine Masculine

Height (m): •

Weight (Kg): •

BMI (BMI = Weight ÷ (Height × Height)): •

Race:

Education Grade:

CLINICAL EVALUATION:

- () Altered heart rhythm () Signs of HF () Dizziness/feeling faint
- () Decrease in exercise tolerance, dyspnea () Transient Ischemic Attack
- () Stroke () Chest pain () Dyspnea at rest
- () Exercise intolerance

Date of Symptom Onset: _____
DD MMM YYYY

other, please specify _____

COMBITIES:

- () Valvular Heart Disorder () Diabetes Mellitus () Hypertension
- () COPD () Hyperthyroidism () TIA/CVA (history)
- () Sudden cardiac death in FH

PREVIOUS PROCEDURES:

- () No Procedures
- () Coronary Angioplasty () Revascularization Surgery () Pacemaker
- () Cardiac Resynchronization Therapy () Valve Prosthesis
- () Implantable cardioverter-defibrillator () Ventricular Assist Device
- () Heart Transplantation () Chemical Cardioversion () Electrical Cardioversion

SMOKING:

Yes No

- () Current (*Consumer for a period not less than 6 months*)
- () Past (*If you have smoked at some point in your life, but have not smoked for more than 6 months*)

DRINKING:

Yes No

- () Current (*Consumer for a period not less than 6 months*)
- () Past (*If you have smoked at some point in your life, but have not smoked for more than 6 months*)

The report or record of consumption of alcoholic beverages, alcoholism and/or alcohol intoxication will be considered in this study. According to the World Health Organization (WHO) acceptable consumption is up to: 15 drinks/week for men and 10 drinks/week for women

ILLICIT DRUGS :

Yes No

Specify: _____

PHYSICAL EXERCISE:

Yes No

Specify: _____

INGESTION OF MEDICINES

Is the subject currently or previously taking any medications, including vitamins and/or supplements?

Yes No

* Record **all** medications on the Concomitant Medications page

MEDICAL HISTORY

Is there any relevant medical history on the following systems?

Code	System	*Yes	No	Code	System	*Yes	No
1	Cardiovascular			9	neoplasm		
two	Respiratory			10	Neurological		
3	Hepatobiliary			11	Psychological		
4	Gastrointestinal			12	Immunological		
5	genito-urinary			13	Dermatology		
6	Endocrine			14	allergies		
7	Hematological			15	Eyes, ear, nose, throat		
8	Skeletal muscle			00	Other		

* If **YES** to any of the above, please enter the code for each condition in the boxes below, provide further details (including dates) and indicate whether the condition is

currently or potentially active. If providing details of surgery, specify underlying cause.
Use a separate line for each condition.

		Currently active?	
Code	Details (including dates)	Yes	No

PHYSICAL EXAMINATION (To be performed only by the medical team)			
Code	System	*Not normal	Normal
1	General appearance		
two	Cardiovascular		
3	Respiratory		
4	Gastrointestinal / Abdomen		
5	extremities		
* If ABNORMAL , enter the code for each condition in the boxes below and provide brief details. Please use one _ line separate for each condition .			
Code	Details		

VITAL SIGNS							
Pulse	
 
 	 	 	
 
 bpm						
Pressure Sanguine (sitting)	
 
 	 	 	
 
 / 
 
 	 	 	
 
 mmHg						

ECG

Normal Not normal **

**

() Sinus () Atrial Fibrillation () Atrial Flutter () Nodal or Atrioventricular Reentry Tachycardia () Wide QRS Tachycardia () Bradyarrhythmias

Store the signed and dated dash in the plastic sleeve on the back of the CRF

LABORATORY ANALYSIS

Initials

Blood for hematology and biochemistry

harvested by

✓	Collection Date (dd mmm yyyy)									
Hematology										
Biochemistry										

Please insert a copy of all results in the plastic sleeve on the back of the CRF.

CONCOMITANT MEDICATION

Medication	Daily Dose (total)	Items	Reason	Start date (MM/DD/YYYY)	End Date (MM/DD/YYYY)	Continuous
				___/___/___ ___/___/___	___/___/___ ___/___/___	
				___/___/___ ___/___/___	___/___/___ ___/___/___	
				___/___/___ ___/___/___	___/___/___ ___/___/___	
				___/___/___ ___/___/___	___/___/___ ___/___/___	
				___/___/___ ___/___/___	___/___/___ ___/___/___	
				___/___/___ ___/___/___	___/___/___ ___/___/___	
				___/___/___ ___/___/___	___/___/___ ___/___/___	

				____ / ____ / ____ ____ / ____ / ____	____ / ____ / ____ ____ / ____ / ____	
				____ / ____ / ____ ____ / ____ / ____	____ / ____ / ____ ____ / ____ / ____	

Study End Date: ____ / ____ / ____
(MM/DD/YYYY)

STUDY CLOSURE FORM

Reason for Terminating Study (Please tick main reason only. Reasons other than Completed Study require explanation next to answer)

Study Concluded

Adverse Event/Severe Adverse Event (**complete the Adverse Event form, if applicable**)

Lost to follow

Participant no compatible

Medication Concurrent

Medication Contraindicated

To remove consent

Death __

Other

5. 2. Term of Loan Responsibility

I, _____, bearer of RG No. _____ UF _____, resident and domiciled at Address _____, No. _____ Bairro _____, City _____, State _____ Tel. With.: _____, Tel. Answer: _____.

I inform, for the due purposes, that I received from **INSTITUTO DO CORAÇÃO/FUNDAÇÃO ZERBINI** registered with CNPJ under no. 50.644.053/0001-13, the equipment described below, owned by **SAMSUNG ELETRÔNICA DA AMAZÔNIA LTDA**., registered with CNPJ 23.209.756/0001-40, for exclusive use in the FAPO-X Samsung project of InovaInCor - InCor, for the term from 30 to 33 day(s) from this date, committing myself to return it in perfect condition at the end of this period.

I declare responsibility for their conservation, in accordance with the manufacturer's recommendations; committing myself not to lend or entrust to another person; and communicate, immediately to the **InovaInCor** via message to us **nº 11 XXXXXXXX, 11 XXXXXXXX** any incident and occurrence with the equipment(s); as well as ensuring the necessary precautions for the proper functioning and integrity of the assigned equipment, it being important to point out that the change of address (equipment) is not authorized without the knowledge and authorization of Inova InCor.

